1.0 TRIAL SUMMARY

[figure not shown]
Abbreviated Title	Pembrolizumab in untreated indolent lymphoproliferative diseases
Trial Phase	II
Clinical Indication	Indolent B-cell non-Hodgkin lymphoproliferative diseases without prior therapy
Trial Type	Nonrandomized, prospective trial
Type of control	None
Route of administration	Intravenous
Treatment Groups	Single group
Number of trial subjects	33
Estimated enrollment period	18 months
Estimated duration of trial	36 months
Duration of participation	18 months

2.0 TRIAL DESIGN

2.1 Trial Design

This is a single arm phase II pilot study evaluating the efficacy of single-agent pembrolizumab for untreated, indolent B-cell non-Hodgkin lymphoproliferative diseases (iBCL) including follicular lymphoma (FL) and marginal zone lymphoma (MZL). In the window phase, treatment will be administered for up to six 3-week cycles and a response assessment performed at the conclusion. Patients that tolerate the drug and meet criteria for an objective response after 6 cycles may continue to receive pembrolizumab for up to an additional 12 cycles in the continuation phase. Patients who show progressive disease or stable disease after 6 cycles may be restaged after 3 additional cycles to assess for pseudoprogression/delayed response. Patients who show disease progression after 3 additional cycles will be removed from treatment. Patients who do not show evidence of disease progression may continue to receive pembrolizumab for up to a total of 18 cycles. A futility analysis will be performed after the first 5 subjects in each of two histologic subgroups (follicular lymphoma, marginal zone lymphoma) are treated. We anticipate that subjects will be enrolled over approximately 18 months and will be followed for outcomes for up to 5 years using standard-of-care assessments.

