4.2.3 Rationale for Endpoints

4.2.3.1 Efficacy Endpoints

Assessing the efficacy of pembrolizumab monotherapy in untreated iBCL will be performed according to standard response criteria (see section 7.2.1.5).

Because of the possibility of pseudoprogression(16), asymptomatic patients whose tumors demonstrate radiologic progression after initial restaging may receive therapy for 3 additional cycles and then will be restaged. Because of possibility of delayed response, patients whose tumors demonstrate stable disease may also receive therapy for 3 additional cycles and then will be restaged. Patients with tumor burden which doubles in size after initial restaging will be considered hyperprogression(17) and will not be eligible for the continuation stage.

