6.0 TRIAL FLOW CHART

6.1 Study Flow Chart

	Screening Period	Treatment Phase			End of treatment ⁶	Long-term Follow-up ⁷
		Window Cycles (1-6)	Response assessment ⁸	Continuation Cycles (7-18) ⁹		
Scheduling and Timing	-42 to -1d	+/- 3d		+/- 3d		
Informed consent	X					
Inclusion/Exclusion criteria	X					
Medical history	X					
Medication review (prior and concomitant)	X	X		X		
Trial treatment administration		X		X		
Post-study anticancer therapy status						X
Survival status						X
Vital signs	X	X		X	X	
Physical exam	X	X		X	X	
ECOG performance status	X	X		X	X	
Adverse event assessment ¹	X	X		X	X	
CBC and differential	X	X	X	X	X	
Comprehensive metabolic panel and LDH	X	X	X	X	X	
HepB SAg, Hep B Core Ab, HepC Antibody and HIV screen	X					
Urinalysis	X					
T3, FT4, and TSH	X	X		X	X	
PT/INR and aPTT	X					
Correlative studies blood draw	X		X		X	
Bone marrow studies ²	X					X
Pregnancy test ³	X					
Tumor assessment ⁵	X	X	X	X	X	
Archival Tissue collection ⁴	X					

¹Adverse events will be recorded from the time of a subject signing consent up until 30 days after the last dose of pembrolizumab, or 90 days after the last dose of pembrolizumab in the case of serious adverse events.

²If bone marrow involvement by iBCL was previously shown then repeat bone marrow exam at screening is not required as it is assumed positive. Otherwise, bone marrow studies include aspirate and unilateral biopsy and should be performed at screening unless a waiver is approved by the study Sponsor-Investigator or sub-Investigator. If all bone marrow studies are negative at screening, these do not need to be repeated. If bone marrow status is unknown or positive at screening, patients will need to have bone marrow study for confirmation of a CR.

³Pregnancy test is only required in women of childbearing potential.

⁴Archived tumor samples are requested for pathologic confirmation and biomarker analysis. If an archived specimen is not available or contains insufficient material, a fresh tumor biopsy (if clinically feasible) will be requested. Correlative studies may be performed on any available tissue.

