⁵Tumor assessment labs and/or imaging (see section 7.1.2.5) will be performed prior to cycle 4 (within 7 days of scheduled treatment dose) during the window phase. Tumor assessment will be performed prior to cycle 7 (within 7 days of scheduled treatment dose) to determine eligibility for continuation on study in continuation phase. Tumor assessment labs and/or imaging will be performed prior to cycles 11 and 15 (within 7 days of scheduled treatment dose) during the continuation phase, as applicable. Tumor assessment labs and/or imaging will be performed at end-of-treatment evaluation only for subjects who did not have tumor assessment labs and/or imaging performed within 60 days of end-of-treatment. Tumor assessment labs and/or imaging will also be performed as indicated per clinical standard of care (e.g. as appropriate for disease, to evaluate clinical suspicion of disease progression). Patients who have stable disease or asymptomatic radiologic disease progression prior to cycle 7 will remain in the window phase with restaging prior to cycle 10 to evaluate for pseudoprogression or delayed response. Patients who have restaging prior to cycle 10 are not required to have tumor assessments prior to cycle 11. Patients who have radiologic disease progression with doubling of tumor size prior to cycle 7 will be categorized as hyperprogression and will not proceed to the continuation phase.

⁶End-of-treatment evaluations should be done within 30 days (+/- 14 days) of the last dose of pembrolizumab or prior to the start of a new anti-cancer drug, whichever is first.

⁷Long-term follow-up should be done according to the patient's physician standard of care. This may be performed at patients' local physician's offices. Long-term follow-up will assess survival and disease progression; for clarification, subjects may be contacted by the study team until death, subject withdrawal of consent, lost to follow-up, or study termination, whichever occurs first.

⁸Response assessment will be performed prior to cycle 7 (within 7 days of scheduled treatment dose) only for those subjects that complete 6 cycles of treatment in the window phase.

⁹During treatment in the continuation phase, clinical assessment (physical exam including performance status, adverse event and medication review) will be performed on day 1 (+/- 3 days) of each odd-numbered cycle only, or as clinically indicated. Studies performed for response assessment⁹ do not need to be repeated prior to cycle 7.

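### Section 2.1 offers three further cycles after progression without the limits set in Section 4.2.3.1 and flow-chart footnote 5, and the phase label for cycles 7-9 is inconsistent

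*Combined protocol and SAP*

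**What the plan says.** **Who may have cycles 7-9.** Section 2.1 puts progressive and stable disease after six cycles together: "Patients who show progressive disease or stable disease after 6 cycles may be restaged after 3 additional cycles to assess for pseudoprogression/delayed response". It then removes patients who progress after those three cycles. Section 4.2.3.1 is narrower on progression: "asymptomatic patients whose tumors demonstrate radiologic progression after initial restaging may receive therapy for 3 additional cycles". It adds that patients whose tumor burden doubles count as hyperprogression and "will not be eligible for the continuation stage".

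**Footnote 5 to the flow chart (Section 6.1)** repeats the narrower rule and adds a phase label. Patients with "stable disease or asymptomatic radiologic disease progression prior to cycle 7 will remain in the window phase with restaging prior to cycle 10". Patients whose tumor doubles before cycle 7 "will be categorized as hyperprogression and will not proceed to the continuation phase". The same footnote says that the assessment before cycle 7 is done "to determine eligibility for continuation on study in continuation phase".

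**Phase boundaries elsewhere.** Section 2.1 caps the window at six cycles. The flow-chart header gives the window column as cycles 1-6 and heads the next column "Continuation Cycles (7-18". Section 7.1.5.2 also gives a six-cycle window. It admits response or stable disease to continuation before cycle 7, with cycle 10 as the alternative for pseudoprogression or delayed response.

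**What the label controls.** Footnote 9 says that clinical assessment in the continuation phase "will be performed on day 1 (+/- 3 days) of each odd-numbered cycle only", or as clinically indicated.

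**The concern.** This rule decides whether a patient whose lymphoma has grown on the study drug receives more of it. Section 4.2.3.1 justifies the three extra cycles by the chance that an apparent progression is not a true one. The limits to asymptomatic patients and to growth short of doubling are the protocol's own safeguards on that chance. Section 2.1, the section that describes the design, omits both.

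The phase label adds a second uncertainty. The doubling rule is worded as exclusion from a phase, not as an instruction to stop the drug, so its force over cycles 7-9 depends on which phase those cycles belong to. On that the protocol gives two answers. A site could follow a sentence in the protocol and still dose a patient whom another section means to take off treatment.

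**Working it through.** The plan gives no figure on this point, so the check is mainly a side-by-side reading.

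**Step 1: who may receive cycles 7-9.**

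| Status before cycle 7 | Section 2.1 | Section 4.2.3.1 | Footnote 5 |
|---|---|---|---|
| Stable disease | permitted | permitted | permitted |
| Asymptomatic progression, no doubling | permitted | permitted | permitted |
| Symptomatic progression | permitted | outside the permission | outside the permission |
| Asymptomatic progression with doubling | permitted | hyperprogression, barred from continuation | fits the window sentence, but hyperprogression, barred from continuation |

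The three places agree on the first two rows and part on the last two. No text says which section prevails.

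**Step 2: which phase cycles 7-9 belong to.**

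- Section 2.1: not window, since the window is at most six cycles.
- Flow-chart header: continuation (7-18).
- Section 7.1.5.2: not window (six cycles). Stable disease may enter continuation before cycle 7.
- Footnote 5: window, for stable disease and asymptomatic progression, until restaging before cycle 10.

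**Step 3: combine the label with the doubling bar.**

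- If cycles 7-9 are continuation, the bar covers them and the drug stops after cycle 6.
- If they are window, the bar as worded first applies after restaging before cycle 10, and nothing express stops cycles 7-9 for an asymptomatic patient whose tumor has doubled.

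**Step 4: whether Section 5.6 settles it.** Its mandatory stop is for confirmed radiographic progression, and the protocol does not define confirmed. If Section 2.1's restaging after three more cycles is the confirmation step, a first progression before cycle 7 is not yet confirmed, so Section 5.6 does not stop cycles 7-9.

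**Step 5: size per affected patient.** Inputs are 200 mg every 3 weeks (Section 5.2, Table 2) and the cycle numbers above, assuming no dose delays.

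- Day 1 of cycle n falls at week 3(n - 1): cycle 7 at week 18, cycle 8 at week 21, cycle 9 at week 24.
- Six window doses: 6 x 200 = 1,200 mg. Cycles 7-9: 3 x 200 = 600 mg. 600/1,200 = 50%.
- Clinical assessments required in cycles 7-9: three under the window label (7, 8, 9) and two under the continuation label (7, 9). The difference is one, at cycle 8.

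**Step 6: the statistical design.** Section 3.1 fixes the primary response rate at the end of six cycles, before any dose in question. For reference, the exact success probability is the sum over x = 5 to 16 of P(X1 = x) P(X2 >= 13 - x), with X1 binomial(16, p) and X2 binomial(17, p). It is 0.902 at p = 0.50, which reproduces the stated 90%. At p = 0.25 it is 0.0449, inside the one-sided 0.05. Neither figure depends on who receives cycles 7-9.

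**The case against.** The best defence is that Section 2.1 is a one-paragraph overview. It says may, it names pseudoprogression and delayed response as its purpose, and two more detailed places agree on how that pathway works. A sensible investigator would follow the detail. Symptomatic patients also have other ways off treatment: Section 5.3.2 removes those who need other anticancer therapy or radiation, and Section 5.6 lets the investigator withdraw a subject. This lowers the chance of harm. It does not remove the conflict, because nothing ranks the sections and those exits depend on individual judgement.

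On doubling, the defence is stronger. A reader might infer from footnote 5 that the protocol authorises cycles 7-9 for patients whose tumor has doubled. The documents do not support that. The natural reading of footnote 5 is a general rule followed by a carve-out. The flow-chart header puts cycles 7-9 in continuation. Section 7.1.2.5.1 requires PET before cycle 7 in follicular lymphoma to decide candidacy for staying on study, with no phase label. Section 7.1.5.2 admits only response or stable disease before cycle 7, although its cycle-10 alternative leaves the phase of cycles 7-9 unstated for progressors. The bar would also do little if it began at cycle 10, since Section 2.1 already removes anyone still progressing then. What remains is an ambiguity created by one label.

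Two further points stand. The 600 mg is also what eligible patients are meant to receive, so it measures the exposure at issue and not an excess across the trial. The monitoring difference is small, because vital signs (7.1.2.3), laboratory review (7.1.3) and the check for events of clinical interest (7.2.3.2) precede every dose under either label.

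**Conclusion.** The inconsistency is real and should be corrected, as a minor point of patient safety and trial conduct. Section 2.1 as written permits doses to symptomatic progressors, whom Section 4.2.3.1 and footnote 5 leave out, and to patients with doubling, whom they are meant to exclude. Footnote 5's window label contradicts three other places and makes the reach of the doubling bar over cycles 7-9 ambiguous. The likely intent is to stop.

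The size is at most three doses per affected patient and one clinical assessment that is or is not required. The number of symptomatic progressors or doublers before cycle 7 cannot be derived from the documents and could be zero. A reader might also infer that the primary result is at risk. It is not, given that Section 3.1 fixes response at the end of six cycles.

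One limit applies. The trial diagram in Section 2.2 is not in the reviewed text. It may show how patients move between phases, so the finding that no express stop exists applies to the written text only.

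**What to change.** One amendment, wording only:

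- **Section 2.1.** Replace the quoted sentence with: *Patients with stable disease, or with asymptomatic progression without doubling of tumor size, at the pre-cycle-7 assessment may receive cycles 7-9 and will be restaged before cycle 10.*
- **Section 4.2.3.1 and footnote 5.** Add: *Symptomatic progression or hyperprogression at the pre-cycle-7 assessment ends pembrolizumab after cycle 6.* The stop then holds whatever the phase is called.
- **Footnote 5, flow chart and Section 7.1.5.2.** Use one phase label for cycles 7-9. Which label is a drafting choice. With continuation, the header and the six-cycle window can stay as they are, but Section 7.1.5.2 must also admit asymptomatic progression without doubling before cycle 7. Footnote 9 should then keep the cycle-8 clinical assessment for patients awaiting restaging before cycle 10, as footnote 5's window label now does.

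The diagram in Section 2.2 should be checked against the new wording. The cost is the amendment and at most one extra routine assessment per affected patient. Sample size, endpoints and analysis do not change. These edits do not define how doubling is measured.

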2.2 Trial Diagram

3.0 OBJECTIVE(S) & HYPOTHESIS(ES)

3.1 Primary Objective & Hypothesis

To gain a preliminary assessment of the efficacy of pembrolizumab as monotherapy for patients with untreated iBCL based on ORR measured at the end of a 6-cycle treatment period.

Hypothesis: Pembrolizumab will have an ORR of $\geq 50\%$ in this untreated population after 6-cycles.

3.2 Secondary Objectives & Hypotheses

(1) Objective:

To assess the safety and toxicity profile of pembrolizumab in patients with untreated iBCL.

Hypothesis: Pembrolizumab will not cause a significant degree of toxicity.

(2) Objective:

To measure the efficacy of pembrolizumab used as monotherapy for patients with untreated iBCL by assessing clinical outcomes including complete response rate (CR), clinical benefit rate (CBR) defined as CR+partial response (PR)+ stable disease (SD) $\times \geq 6$ months, time to next therapy (TNT), progression-free survival (PFS), and the duration of response (DOR).

3.3 Exploratory Objectives

(1) Objectives:

To evaluate clinical features including, as applicable, the follicular lymphoma international prognostic index (FLIPI) (see appendix 11.5), in addition to standard-of-care biomarkers including cytogenetics and Ki67 and correlate with response to pembrolizumab.

To evaluate baseline expression of proteins in the PD-1 pathway in archived tumor specimens and in pretreatment peripheral blood mononuclear cells and correlate with response to pembrolizumab.

To measure peripheral blood T-cell subsets and correlate with response to pembrolizumab.

4.0 BACKGROUND & RATIONALE

4.1 Background

B-cell non-Hodgkin lymphoproliferative diseases (BCL) are categorized according to how aggressively they behave. The indolent BCL subtypes (iBCL) include CLL/SLL, FL, MZL, WM/LPL, and, in some circumstances, MCL (1). Owing to immune activation, the early course of iBCL often is characterized by minimal progression or even spontaneous remission. The contribution of immune modulation in the natural history and treatment of iBCL has been borne out in preclinical studies (2) and early phase clinical trials (3-5).

iBCL inevitably relapse after therapy and typically become increasingly refractory to available treatments over time; iBCL are considered incurable short of allogeneic stem cell transplantation. Improving on this paradigm is necessary and requires novel strategies that minimize toxicity.

Anti-cancer therapies historically render the greatest benefit in the first-line treatment setting. This can be attributed to relatively undeveloped drug-resistance mechanisms in tumors and their smaller volume, in addition to the contribution of host immunity (6). The relatively slow early progression of iBCL makes this disease well suited to testing novel, low-toxicity treatment approaches in a predefined “window” of time (7).

4.1.1 Pembrolizumab: Pharmaceutical and Therapeutic Background

The importance of intact immune surveillance in controlling outgrowth of neoplastic transformation has been known for decades (8). Accumulating evidence shows a correlation

between tumor-infiltrating lymphocytes (TILs) in cancer tissue and favorable prognosis in various malignancies (9). In particular, the presence of CD8+ T-cells and the ratio of CD8+ effector T-cells / FoxP3+ regulatory T-cells seems to correlate with improved prognosis and long-term survival in many solid tumors.

The PD-1 receptor-ligand interaction is a major pathway hijacked by tumors to suppress immune control. The normal function of PD-1, expressed on the cell surface of activated T-cells under healthy conditions, is to down-modulate unwanted or excessive immune responses, including autoimmune reactions. PD-1 (encoded by the gene *Pdcd1*) is an Ig superfamily member related to CD28 and CTLA-4 which has been shown to negatively regulate antigen receptor signaling upon engagement of its ligands (PD-L1 and/or PD-L2) (10). The mechanism by which PD-1 down modulates T-cell responses is similar to, but distinct from that of CTLA-4 as both molecules regulate an overlapping set of signaling proteins. PD-1 was shown to be expressed on activated lymphocytes including peripheral CD4+ and CD8+ T-cells, B-cells, Tregs and Natural Killer cells. The ligands for PD-1 (PD-L1 and PD-L2) are constitutively expressed or can be induced in a variety of cell types. Binding of either PD-1 ligand to PD-1 inhibits T-cell activation triggered through the T-cell receptor. Although healthy organs express little (if any) PD-L1, a variety of cancers were demonstrated to express abundant levels of this T-cell inhibitor. This suggests that the PD-1/PD-L1 pathway plays a critical role in tumor immune evasion and should be considered as an attractive target for therapeutic intervention.

Pembrolizumab is a potent and highly selective humanized monoclonal antibody (mAb) of the IgG4/kappa isotype designed to directly block the interaction between PD-1 and its ligands, PD-L1 and PD-L2. Pembrolizumab has recently been approved in the United States for the treatment of patients with unresectable or metastatic melanoma and disease progression following ipilimumab and, if BRAF V600 mutation positive, a BRAF inhibitor.

4.1.2 Preclinical and Clinical Trial Data

Refer to the Investigator's Brochure for Preclinical and Clinical data.

4.2 Rationale

4.2.1 Rationale for pembrolizumab in lymphoma

As evidenced by the subset of patients with apparent spontaneous disease regression, the host immune system can play a significant role in iBCL (11, 12). Programmed cell death-1 (PD-1) is an immune checkpoint receptor expressed on activated T-cells. Tumor cells including lymphoid malignancies have been shown to express the ligands of PD-1: PD-L1 and PD-L2 (13). Engagement of T-cell PD-1 by its ligands downregulates T-cell activity through exhaustion. Modulation of the immune checkpoint pathway in iBCL has shown some promise in the relapsed and refractory setting in which the monoclonal PD-1 receptor blocking antibody nivolumab demonstrated activity as a single agent with an ORR in 4 of 10 patients treated in a phase I study (4). In a separate study the monoclonal anti-PD-1 antibody pidilizumab was combined with rituximab in patients with relapsed or refractory follicular lymphoma and

demonstrated an ORR in 19 or 29 patients (66%) with a median time to observed response of 88 days (range, 53 – 392) (5).

Pembrolizumab is a humanized monoclonal antibody of PD-1 with high affinity and potency. To date, pembrolizumab has shown an excellent safety and toxicity profile (see investigator's brochure), thereby fulfilling an important criterion for its use in the first-line window-of-opportunity setting (7). Use of immune checkpoint modulating antibodies as mono-therapy in the first-line setting has demonstrated efficacy in solid tumors (14, 15). Compared with the relapsed and refractory setting, untreated iBCL is accompanied by a relatively intact host immune repertoire with a potentially greater capacity to mount an effective anti-tumor immune response with immune-checkpoint inhibitor therapy.

